8.3. INTERCURRENT EVENTS AND MISSING DATA

All possible efforts will be made to minimize missing data.

Unless specified otherwise, screen values or pre-dose unscheduled measurements may be used as a baseline value in the event of missing Day 1 pre-dose measurements.

The original data will always be presented in the listings.

8.3.1. Efficacy Data

As missing data may potentially bias the outcome of the statistical analyses and the subsequent estimation of the magnitude of the treatment effect, different strategies will be applied to provide a balanced assessment of treatment efficacy. This section discusses intercurrent events and missing data in general, but details for each endpoint are discussed in [Section 10](#).

Intercurrent Events

The following potential intercurrent events are currently identified:

- Discontinuation of study treatment
- Specifically, for the 12MWT and 30STS; unwilling or unable to perform the test or walk for the full 12 minutes due to reasons at least possibly related to PMM or study treatment

Subjects who discontinue treatment will be encouraged, where appropriate, to continue in the study with a reduced assessment schedule at Weeks 12 and 24. As a minimum they will be requested to complete the 12MWT and MFIS efficacy assessments at these visits. This allows a treatment policy strategy to be used; for example, the distance walked at the relevant visit will be included in the analysis, regardless of whether the subject has previously discontinued study treatment.

If the subject is unable to perform the 12MWT and/or 30STS at a visit, for reasons at least possibly related to their PMM, their data will be imputed as 0 meters and/or 0 sit to stands for each test, respectively. To assess the subject as unable to perform the 12MWT there must be clear evidence that the subject is not ambulatory at the time of the test.

If the subject is still ambulatory, and therefore able to do the test, then consideration should be given to whether the subject is unwilling to perform the test, or prevented from (e.g., specialty clinic visit that prevents attending the study visit) performing the test due to reasons possibly related to PMM or study treatment. If the subject is still ambulatory but unwilling to perform the 12MWT, or prevented from doing the test, their distance will be imputed using a worst case imputation; unless the reason is unrelated to PMM or study treatment. The change from baseline distance will be imputed using a random draw from the normal distribution with a mean equal to the worst change from baseline reported over the study across both treatment groups, and the standard deviation for the raw changes from baseline at the relevant visit irrespective of treatment group. These values will only be determined from those assessments where subjects have walked for the full 12 minutes (i.e., those assessments where there were no intercurrent events). Twenty-five imputations will be made to match the multiple imputations mentioned below for missing data. The imputations will be restricted to ensure the value for the visit is ≥ 0 meters for the visit.

The same approach as detailed above in the previous paragraph, will be taken for subjects who discontinue study treatment and do not continue in the study; unless the reason for discontinuing from the study and withdrawing from the study are unrelated to their PMM or study treatment (e.g., site unable to continue having visits during pandemic). The special exception to this will be death; if a subject dies their 12MWD will be imputed as 0 meters.

If the subject attempts the 12MWT or 30STS test but stops the test prematurely due to reasons at least possibly related to their PMM their data recorded will be used in all analyses. Examples of reasons for incomplete tests which will be considered related to the subject's PMM include fatigue, weakness, tiredness, exhaustion or pain in limbs. In this situation it is assumed that the subject has walked as far as they could in the 12 minutes and the data is not regarded as missing.

An independent blinded adjudication committee will review the 12MWT cases. The structure, function and operation of the adjudication committee will be detailed in a separate charter.

Missing PROMIS T-scores as a result of an intercurrent event considered related to a subject's PMM or study treatment will also be imputed using worst case imputation. A blinded Reneo team will adjudicate these cases.

A blinded Reneo team will also adjudicate whether the subject stops their 30STS test prematurely for reasons at least possibly related to their PMM.

Adjudication decisions will be made and documented prior to database locking and the randomization being unblinded.

Missing data

Missing data may arise for the following reasons:

- Withdrawal from the study
- Specifically, for the 12MWT and 30STS; unwilling or unable to perform the test or walk for the full 12 minutes due to reasons unrelated to their PMM or study treatment

The reasons for not performing a test or stopping it prematurely will be collected. Only reasons which clearly indicate that it was unrelated to the subject's PMM or study treatment will be assigned unrelated. The following are examples of why the reason may be regarded as unrelated to the subject's PMM:

- Site is unable to perform the test at the visit
- Subject suffers an accidental injury prior to the visit with clear evidence the subject's PMM and study treatment did not contribute to the injury
- Unexpected fire alarm at the study center means the test has to be aborted

The independent blinded adjudication committee will review all reasons for missing or incomplete 12MWTs and adjudicate whether the reason was related to the subject’s PMM or study treatment. The committee will also adjudicate whether a subject is unable or unwilling to perform a test.

Missing data assessed as unrelated to a subject’s PMM or study treatment will be considered missing at random (MAR). Missing scores (as opposed to intercurrent events) will be handled using either multiple imputation or through mixed effect models for repeated measures (MMRM). Where multiple imputations are used along with imputations for intercurrent events, the multiple imputation step will be performed prior to imputations for intercurrent events. Hence, the MAR imputations will be replaced with those for intercurrent events where applicable.

The table below summarizes the imputation used for the intercurrent and missing data scenarios for the 12MWT:

Type	Case	Handling of Data
Intercurrent Event	Discontinuation of study treatment only; 12MWT still completed	No imputation required. Use 12MWD recorded
	Unable to perform the test for reasons possibly related to PMM or study treatment. Subject is not ambulatory at time of assessment.	0
	Unable to walk the full 12 minutes for reasons possibly related to PMM or study treatment*	Use 12MWD recorded
	Ambulatory subject unwilling to, or prevented from, performing the test for reasons possibly related to PMM or study treatment	Worst case multiple imputation
	Withdrawal from study for reasons possibly related to PMM or study treatment	Worst case multiple imputation
	Death	0
Missing Data	Unable to perform the test, or walk the full 12 minutes, for reasons unrelated to PMM or study treatment e.g., COVID-19	Multiple imputation (MAR cases)
	Unwilling to perform the test for reasons unrelated to PMM or study treatment	
	Withdrawal from study unrelated to PMM or study treatment	

* Note: This is the only adjudication decision where the distance walked for subject’s unable to walk the full 12 minutes is used in the analyses. For all other decisions the distance is set to missing prior to analyses.

Multiple Imputation

Missing values will be imputed with the SAS[®] MI procedure. Prior to imputation the missing data pattern will be assessed. To account for non-monotone missingness (i.e., for the 12MWT this would be where a subject has missing data for Week 12, but has data for Week 24), a Markov Chain Monte Carlo (MCMC) model will be used to impute the non-monotone missing data, followed by a sequential regression model to impute the remaining data. Randomization seed numbers will be specified for each part of the imputation to ensure consistency and repeatability.

In the non-monotone procedure, means and variances from the available data will be used to determine the MCMC starting values; imputed values will be selected with maximum likelihood methods. Initially, 200 MCMC runs will be generated before selecting the first imputed data set. An additional 24 data sets will be generated to reflect the uncertainty due to missing values. The 25 datasets will be separated by 100 iterations of the MCMC. The number of datasets may be increased if the analyses are not found to be sufficiently stable with respect to p-values. Stability will be determined if the p-values are the same to the second decimal place after 3 repetitions. These imputations will be performed separately within each treatment group. The imputation model will include the same covariates as for the analysis model and the value at each scheduled time point. Thus, for the primary endpoint the model will include the stratification mutation factor (in the event of a mis-stratification, the actual value recorded on the database will be used) and the scheduled time points (Screening, Baseline, Week 12 and Week 24). Imputed values will be restricted to being plausible i.e., for the primary endpoint values will be restricted to ≥ 0 meters, and for the secondary endpoint PROMIS T-score will be restricted to ≥ 30.3 and ≤ 83.6 .

In the scenario where a subject has a missing baseline (either not collected or out of window) and the screening value is used as the baseline value, the multiple imputation model will preserve the time the data was collected. So in this scenario the screening value will be present and the baseline value will be missing and imputed. The imputed baseline values will only be used to facilitate the imputation of later visits and will not be used in the analyses. After imputation the imputed baseline values will be replaced with the observed screening value which will be used in the calculation of changes from baseline and analyses (e.g., as a covariate).

The resulting 25 datasets will then be passed through the sequential regression models to impute for monotone missing data. If the non-monotone procedure is not required 25 datasets will be generated from the monotone imputation.

Each of the 25 datasets will be analysed and the results obtained will be combined using the SAS[®] MIANALYZE procedure, based on Rubin's imputation rules (Rubin 1987⁵), to produce pooled estimates of the treatment difference, along with their standard errors, 95% confidence intervals, and associated p-values.

The PGIC endpoints are discrete variables with 7 levels collected once at the end of the study, so for these endpoints an ordinal logistic regression model will be used to impute monotone missing data. The imputation model will include the same covariates as for the analysis model and 25 datasets will be imputed. Imputed values will be restricted to being plausible i.e., between -3 and 3.

The PGIS endpoints are discrete variables with 5 levels collected at visits throughout the study, for these endpoints an ordinal logistic regression model will be used to impute missing data. If the data is non-monotone, then the Fully Conditional Specification (FCS) logistic regression method in SAS[®] MI procedure will be used. The imputation model will include the same covariates as for the analysis model and 25 datasets will be imputed. Imputed values will be restricted to being plausible i.e., between 1 and 5.

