8.5 Efficacy Analyses

8.5.1 Primary Endpoint

The changes from baseline in distance walked during the 12MWT for the FAS will be analyzed using a MMRM. The model will include fixed terms for treatment, visit and the treatment-by-visit interaction. The model will also include the stratification mutation factor and continuous baseline distance walked during the 12MWT as covariates. An unstructured covariance structure will be used for the repeated visits within a subject. The Kenward-Rogers approximation (Kenward & Roger 1997) will be used to estimate the denominator degrees of freedom. The treatment comparison (REN001 100mg - placebo) for the change from baseline at both Weeks 12 and 24 will be estimated. The estimates, standard errors, 95% confidence intervals and associated p-values will be presented. The primary comparison is Week 24.

Intercurrent Events

The following potential intercurrent events are currently identified:

- Discontinuation of study drug
- Inability to perform the test or stopping the test prematurely due to reasons at least possibly related to PMM

A treatment policy strategy will be used; hence the distance walked at the relevant visit will be included in the analysis, regardless of intercurrent events. If the subject is unable to perform the test a distance of 0 meters will be imputed for the visit.

Using this treatment policy strategy, the estimand is defined as the difference in means between the treatments in the target patient population for the change from baseline at Week 24 in 12MWD, regardless of whether or not the subject continues with treatment or is unable to walk for 12 minutes.

Missing data

All possible efforts will be made to ensure that subjects complete all the required assessments. Subjects who discontinue study drug will be encouraged, where appropriate, to continue with reduced assessments at the Week 12 and Week 24 visits (see Section 3.6). However missing data may arise for the following reasons:

- Withdrawal from the study
- Unable to perform the test for reasons unrelated to their PMM (e.g., site unable to perform the test at the visit, or the subject suffers an accidental injury prior to the visit)
- Unable to walk for 12 minutes for reasons unrelated to their PMM (e.g., unexpected fire alarm at the study center means the test has to be aborted)

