For the primary analysis the data will be considered as MAR. Missing scores (as opposed to intercurrent events) will be imputed using the technique of multiple imputations. The multiple imputation step will be performed prior to any fixed imputations.

Each dataset with complete data for each subject will be analyzed using the MMRM model described above and the results obtained will be combined using Rubin's imputation rules (Rubin, 1987) to produce pooled estimates of the treatment difference, along with their standard errors, 95% confidence intervals, and associated p-values.

As rules for handling intercurrent events and missing data may potentially bias the outcome of the statistical analyses and the subsequent estimation of the magnitude of the treatment effect, sensitivity analyses will be conducted to provide a balanced assessment of treatment efficacy.

The following sensitivity analyses will be conducted:

- a pattern-mixture multiple imputation approach where missing data from subjects who receive either treatment will be assumed to follow a similar trajectory to those in the placebo group.
- a tipping point analysis (O'Kelly & Ratitch, 2014) will be used, imputing different changes from baseline for the missing data.

In addition, the primary analysis will be replicated using the PP set.

A while on-treatment policy strategy will also be employed in a supplementary analysis utilizing only the on-treatment measurements for each subject. All missing data will be taken as MAR and so a MMRM will be used, without multiple imputation. As all subjects would be required to have at least one post-baseline on-treatment measurement this analysis will use the modified analysis set.

All model assumptions will be checked by evaluating model residuals. If the evaluation of residuals indicates a problem with the model assumptions, a transformation of the data or non-parametric analyses may be considered.

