2. INTRODUCTION

This Statistical Analysis Plan (SAP) details the statistical analyses for the REN001-201 (STRIDE) study and the sub-study REN001-201-DXA. REN001-201 is a 24-week double blind, randomized placebo-controlled study, designed to assess the efficacy and safety of mavodelpar (REN001) in patients with Primary Mitochondrial Myopathy (PMM). REN001-201-DXA is an exploratory sub-study to REN001-201, designed to assess changes in bone mineral density (BMD), using Dual Energy X-ray Absorptiometry (DXA) scans, after 24 weeks of treatment with mavodelpar.

The purpose of this SAP is to ensure that the data listings, summary tables and figures which will be produced, and the statistical methodologies that will be used, are comprehensive and appropriate for the assessment of study objectives specified in the study protocols. Changes from the analyses specified in the protocol will be identified in the SAP and any amendments to the SAP will be made prior to database lock. Any additional analyses not described in the final SAP or deviations from the final SAP will be documented in the clinical study report (CSR).

The SAP has been developed based on REN001-201 Protocol Version 4.0, REN001-201-DXA Protocol Version 2.0 and the latest CRF available (Version 5.0, Date 17 November 2021). The subsequent country specific protocol amendments for REN001-201 (see Appendix 2) do not impact the SAP.

The analysis of this study will occur after all subjects have had the ability to complete REN001-201 and the REN001-201-DXA sub-study (as applicable), the data has been cleaned and the database locked and unblinding has occurred.

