10.1. PRIMARY ENDPOINT

10.1.1. Primary Estimand

The primary estimand of interest for this study involves a treatment policy strategy. Using this treatment policy strategy, the primary estimand for the primary endpoint is defined as the difference in means between the treatments in the target patient population for the change from baseline at Week 24 in 12MWD, regardless of whether or not the subject continues with treatment or is unable to walk for 12 minutes.

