10.1.2. Primary Analysis

Intercurrent events and missing data will be handled using the methodology described in [Section 8.3.1](#). For the primary endpoint the missing values will be imputed using the technique of multiple imputations; this includes incomplete tests considered unrelated to their PMM, which will be set to missing prior to imputation. The multiple imputation step will be performed prior to any imputations for intercurrent events.

Changes from baseline will be analysed using a MMRM. The model will include fixed terms for treatment, visit and the treatment-by-visit interaction. The model will also include the stratification mutation factor and continuous baseline distance walked during the 12MWT as covariates. An unstructured covariance matrix will be used for the repeated visits within a subject and the model will allow the covariance matrix to differ between treatment groups. If this analysis fails to converge, then an analysis of covariance (ANCOVA) will be used which will analyse the change from baseline at Week 24 and at Week 12 separately. The ANCOVA model will include a fixed term for treatment and the mutation stratification factor and continuous baseline distance walked during the 12MWT as covariates. The Kenward-Rogers approximation will be used to estimate the denominator degrees of freedom ([Kenward 1997](#)). The treatment comparison (mavodelpar 100mg - placebo) for the change from baseline at both Week 12 and Week 24 will be estimated. The estimates, standard errors, 95% confidence intervals and associated p-values will be presented for each of the multiple imputation analyses as well as the pooled values.

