14. CHANGES FROM PLANNED ANALYSES SPECIFIED IN THE PROTOCOL

- The secondary endpoints have been updated following FDA advice. The PROMIS T-score has been promoted to a secondary endpoint and MFIS physical sub-scale score and PGIC (muscle symptoms) have been moved to exploratory endpoints. The order of testing of endpoints has also been updated to align with this change.
- As the PGIC is assessed at the end of study treatment (Week 24 or Early Termination) a while on treatment strategy was proposed in the protocol. However, with some subjects not completing their PGIC assessment until more than a week after their last dose of study medication the strategy has been changed. The primary analysis will include all recorded data, regardless of the duration between the subject's last dose of study medication and the assessment. Given some subjects will have been off treatment for more than 7 days before recording PGIC, this analysis will no longer be referred to as a 'while on treatment' strategy; instead, this is a 'treatment policy' strategy. Subjects with no PGIC assessment will be considered as missing unless the incidence of missing PGIC data exceeds 5%. If the incidence exceeds 5% a multiple imputation approach will be used. A 'while on treatment' strategy has also been included as a supplementary analysis, where only assessments within 7 days of the last dose of study treatment will be included.
- A responder endpoint has been defined for the PGIC muscle symptoms and PGIC fatigue symptoms in addition to the 7-point scale endpoints.
- Two additional exploratory endpoints based on the 12MWD have been defined to further support the primary analysis. The endpoints are the first and last 6-minute periods of the 12MWD and aim to investigate whether there is a difference in treatment effect in these two periods.
- The supplementary analysis for the primary endpoint using a while on treatment strategy has been updated to an ANCOVA following review comments from the FDA. The original while on treatment analysis proposed in the protocol is now referred to as a treatment period restricted analysis.
- Added the exploratory endpoint for the phenotypic description questions (exercise tolerance, gait stability and myopathy) which are asked at Baseline and Week 24.

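### SAP 10.1.1 states a treatment-policy estimand, but the primary analysis gives related withdrawals, refusals and prevented tests worst-case values, a change from the protocol that Section 14 omits; separately, the 12MWD and 6-minute rules for some stopped walks disagree

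*SAP*

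**What the plan says.** **Estimand.** SAP 10.1.1 names a treatment-policy strategy and defines the effect "regardless of whether or not the subject continues with treatment or is unable to walk for 12 minutes". It mentions no other strategy.

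**Handling in the primary analysis.** SAP 10.1.2 sends intercurrent events and missing data to 8.3.1. The text and table there give:
- study drug stopped but 12MWT done, or a walk cut short for related reasons: recorded distance used;
- not ambulatory for related reasons: 0 m;
- death: "if a subject dies their 12MWD will be imputed as 0 meters";
- ambulatory but unwilling or prevented for related reasons, and related study withdrawal: a normal draw "with a mean equal to the worst change from baseline reported over the study across both treatment groups", with the visit SD pooled over arms and a floor of 0 m;
- unrelated reasons: multiple imputation under MAR.

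Related means possibly related to PMM or study treatment. A reason counts as unrelated only when that is clear, so doubtful cases go to the related side.

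**Protocol.** Section 8.5.1 lists two intercurrent events: stopping study drug, and PMM-related inability to do or finish the test, with 0 m if the test cannot be done. Study withdrawal stands in the other list, introduced by "However missing data may arise for the following reasons", and the rule is "For the primary analysis the data will be considered as MAR". Death has no rule.

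**Change list.** SAP Section 2 says "Changes from the analyses specified in the protocol will be identified in the SAP". On handling for the primary endpoint, Section 14 reports only that "The supplementary analysis for the primary endpoint using a while on treatment strategy has been updated to an ANCOVA".

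**Stopped walks.** The footnote to the 8.3.1 table sets the recorded distance to missing for every incomplete walk except those adjudicated unable for related reasons. SAP 10.1.2 says of the multiple imputation: "this includes incomplete tests considered unrelated to their PMM, which will be set to missing prior to imputation". SAP 10.3.9 gives the example of a 10-minute walk adjudicated as unwilling or prevented for related reasons. For the 6-minute endpoints it keeps the first 6 minutes and imputes only the last 6.

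**The concern.** Giving a subject a poor value because an event occurred is a composite-type strategy. A reader of 10.1.1 would take the primary result as the effect whatever happened to treatment. For these subjects it contains a penalty whose size is set by one extreme observation. The estimand sentence is nearly the protocol's, while the handling beneath it has moved from MAR to worst case for part of the withdrawals. Section 14 explains and relabels a comparable change for PGIC, now exploratory, but not this one for the primary endpoint.

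The second issue is internal agreement. SAP 4.1 defines the last-6-minute distance as the total minus the first 6 minutes. If the total is redrawn with a floor of only 0 m while the first 6 minutes are kept as walked, the two analysed distances can contradict each other.

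**Working it through.** **1. Plan's own figure.** Inputs from SAP 3.5: effect 60 m, SD 125 m, two-sided 5%, 93 per arm. The noncentrality is 60 / (125 × √(2/93)) = 3.27, and the two-sample t-test power is 90.25%. The stated 186 subjects and 90% reproduce.

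**2. Size of the penalty.** The documents give no worst change. Assume 2 arms × 93 subjects × 2 visits = 372 full walks with independent normal changes. The expected minimum is then about -348 m (effect 60 m) to -369 m (no effect) at SD 125 m, and about -277 to -295 m at SD 100 m. I use W = -345 m as the main case, with -250 and -150 m as milder ones.

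**3. Effect on the primary contrast.** Let a and b be the shares with related withdrawal, refusal or a prevented test on REN001 and placebo. Ignoring the 0 m floor,

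expected difference = [(1 − a) × 60 + a × W] − b × W.

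For a = 5%, b = 2%, W = -345: (57.00 − 17.25) − (−6.90) = 46.65 m.

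| Related loss, REN001 / placebo (assumed) | W = -150 | W = -250 | W = -345 |
|---|---|---|---|
| 5% / 2% | 52.5 m | 49.5 m | 46.7 m |
| 2% / 5% | 63.3 m | 66.3 m | 69.2 m |
| 7% / 7% | 55.8 m | 55.8 m | 55.8 m |

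If these subjects were like the others in their arm (MAR), the answer would be 60 m in every cell. One percentage point of loss on REN001 costs (60 − W)/100, which is 2.1 m at W = -150 and 4.05 m at W = -345. One point on placebo adds −W/100, which is 1.5 m and 3.45 m.

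A simulation of the whole procedure (100 per arm, SD 125 m, worst change taken from the simulated data, 25 imputations, ANCOVA, Rubin's rules, 1,500 replicates) agrees. At 5% / 2% it gives 47.0 m, against 59.8 m under MAR. At 2% / 5% it gives 69.2 m against 60.9 m. With no true effect and 7% loss in both arms, rejection was 3.6%.

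**4. Stopped walk, total against first 6 minutes.** Assume a baseline of 600 m, even pace and a stop at 10 minutes. The recorded distance is 600 × 10/12 = 500 m, and the first 6 minutes are 300 m (15 laps of 20 m). The 12MWD is redrawn from N(600 + W, SD) truncated at 0:

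P(12MWD < 300) = [Φ((300 − 600 − W)/SD) − Φ(−(600 + W)/SD)] / [1 − Φ(−(600 + W)/SD)].

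| W, SD | P(12MWD < 300 m) | P(12MWD < 500 m) |
|---|---|---|
| -150, 125 | 11.5% | 65.5% |
| -250, 125 | 34.3% | 88.5% |
| -345, 125 | 63.3% | 97.4% |
| -276, 100 | 40.5% | 96.1% |

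The contradiction is possible in every row. How often depends almost wholly on the assumed worst change.

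**5. The three rules side by side.** The 8.3.1 text keeps the data of a test stopped for PMM-related reasons. The 8.3.1 footnote keeps them only under the unable-and-related decision. The 10.3.9 example puts a started walk under the unwilling-or-prevented decision, so its total is discarded. All three cannot describe one consistent treatment of a related stop.

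**The case against.** The strongest reply is that nothing is hidden. The rule is written out in 8.3.1, tabulated case by case and invoked by 10.1.2. Section 2 promises identification in the SAP without naming Section 14, and the protocol leaves full analysis details to the SAP. An analyst would run the intended analysis unchanged. That stands, so this is not an undisclosed analysis. But the estimand statement still describes a different quantity, and 8.3.1 does not mark its rules as departures from the protocol. The version history mentions worst-case imputation only as a change between SAP versions.

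Mitigation also stands. The tipping-point analysis in 10.1.4 starts from MAR, and the treatment-period-restricted analysis in 10.1.5 assumes it. They show the sensitivity but do not correct 10.1.1.

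On stopped walks, a reader might infer that 8.3.1 breaks its own rule that imputed values be plausible. It does not: for this endpoint the SAP defines plausible as at least 0 m. It can also fairly be said that a worst-case value is a deliberate penalty, not a prediction. That weakens any complaint about totals below the metres walked, but not the disagreement between two endpoints taken from one walk.

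A reader might also want every redrawn value truncated at the recorded distance. For unrelated stops this would do harm. With the 600 m example the MAR draw is already centred on the 600 m that an even pace implies, and truncation at 500 m would push the average above it.

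**Conclusion.** The point holds as a mismatch between the stated estimand and the primary analysis, with an incomplete list of changes from the protocol. The size is conditional. At an assumed 5% against 2% related loss and a true effect of 60 m, the primary estimate is about 47 m for a worst change near -345 m and 52.5 m for -150 m. With the loss reversed it is about 69 m and 63 m. The 60 m comparator assumes that the lost subjects resemble those observed. The documents state no related-loss rate, worst change or count of stopped walks.

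The stopped-walk inconsistency is real but probably rare, because walks stopped for fatigue, weakness, tiredness, exhaustion or limb pain keep their recorded distance.

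Three stronger inferences are not supported. Type I error is not shown to be inflated: with no effect and equal loss the expected difference is zero, and simulated rejection was 3.6%. The sample size is not wrong: 93 per arm reproduces 90%. The worst-case rule is not invalid in itself: it is a legitimate choice once named. Severity: minor to should-fix.

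**What to change.** 1. **SAP 10.1.1.** State three strategies: treatment policy for study-drug discontinuation with a 12MWT obtained and for related incomplete walks; the worst-case, composite-type strategy for related withdrawal, refusal and prevented tests; 0 m for non-ambulatory subjects and for death.
2. **SAP 8.3.1 lists.** Align them with the table: add related withdrawal to the intercurrent events, and limit withdrawal under missing data to unrelated reasons.
3. **SAP Section 14.** List the move of related withdrawal from MAR to worst case, the rule for refused or prevented tests, the extension to reasons related to study treatment, and the death rule.
4. **Attempted walks with a related stop.** Reconcile the 8.3.1 text, its footnote and 10.3.9 so that the 12MWD and the 6-minute endpoints agree. One way is to build the 12MWD of such a walk, when it lasted more than 6 minutes, as the recorded first 6 minutes plus the imputed last 6, as 10.3.9 and the definition in 4.1 already imply.

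Leave the MAR imputation of unrelated aborted walks as it is, and leave SAP 3.5 unchanged.

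The cost is wording and one programming step before unblinding, with no extra subjects, visits or analyses. The estimand text gets longer. Item 4 makes the penalty smaller for those few walks. It guarantees a total no smaller than the first-6-minute distance, though the total may still fall below the metres walked when the test stopped.
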